
Table of In-Text Figures

Figure 1	Overall Trial Design	20
Figure 2	Design of the Trial	20

List of Abbreviations

AE	Adverse event
AESI	Adverse events of special interest
ALT	Alanine aminotransferase
ALU	Aluminum
AST	Aspartate aminotransferase
AUC	Area under the plasma concentration-time curve
AUC _{0-∞}	Area under the plasma concentration-time curve from time zero (= dosing time) extrapolated to infinity
AUC _{0-t}	Area under the plasma concentration-time curve from time zero (= dosing time) to the last sampling time (t_{last}) at which the concentration is at or above the lower limit of quantification.
AUC _{extra}	The AUC from time t_{last} extrapolated to infinity
AUC _{extra%}	AUC _{extra} / AUC _{0-∞} in percent
beta-HCG	Beta-human chorionic gonadotropine
BMI	Body mass index
CI	Confidence interval
CK-MB	Creatine phosphokinase - myocardium/brain type
CL/f	Apparent total body clearance considering the fraction of dose (f) absorbed
C _{max}	Maximum plasma concentration
c-Met	Mesenchymal-epithelial transition factor
CRO	Contract research organization
CTCAE	Common Terminology Criteria for AEs
CV	Coefficient of variation
ECG	Electrocardiogram
eCRF	Electronic case report form
eGFR	Estimated glomerular filtration rate
EMA	European Medicines Agency
EudraCT	European Union Clinical Trials Register
FDA	Food and Drug Administration
GCP	Good Clinical Practice
GeoMean	Geometric mean

GMR	Geometric Mean Ratio
h	Hour(s)
HCC	Hepatocellular carcinoma
HGF	Hepatocyte growth factor
HIV1/HIV2	Human immunodeficiency virus 1 and 2
IB	Investigator's Brochure
ICF	Informed Consent Form
ICH	International Council for Harmonisation
IEC	Independent Ethics Committee
IMP	Investigational Medicinal Product
LLOQ	Lower limit of quantification
min	Minute(s)
NCI	National Cancer Institute
NSCLC	Non-small cell lung cancer
PGx	Pharmacogenetics
PK	Pharmacokinetics
QTcF	Corrected QT interval according to Fridericia
SAE	Serious adverse event
SAP	Statistical Analysis Plan
SD	Standard deviation
SUSAR	Suspected unexpected serious adverse reactions
T/R	Test/Reference
$t_{1/2}$	Terminal half-life
TEAE	Treatment emergent adverse event
TF1; TF2; TF3	Tablet Formulation 1; Tablet Formulation 2; Tablet Formulation 3
t_{last}	The last sampling time at which the concentration is at or above the lower limit of quantification
t_{max}	Time to reach the maximum plasma concentration
ULN	Upper limit of normal range
V_z/f	Apparent volume of distribution during terminal phase (after oral/extravascular administration)

1 Synopsis

Clinical Trial Protocol Number	MS200095_0038
Title	An open-label, single-dose, randomized, 2 period, 2-sequence cross-over, single-center Phase I trial in healthy subjects to assess the bioequivalence of tepotinib tablet formulation 3 administered as 5 tablets of 100 mg versus 2 tablets of 250 mg dose strength.
Trial Phase	1
IND Number	Not applicable
FDA covered trial	No
EudraCT Number	2019-003578-13
Principal Investigator	PI PI Germany
Sponsor	Merck Healthcare KGaA, an affiliate of Merck KGaA, Darmstadt, Germany, [name]
Trial center	PI Germany
Planned trial period (first subject in-last subject out)	October to December 2019
Trial Registry	ClinicalTrial.gov, EU Clinical Trials Register
Primary Objectives:	

 • To demonstrate bioequivalence between 5 tablets of the 100 mg dose strength of tepotinib tablet formulation 3 (TF3, test treatment) and 2 tablets of the 250 mg dose strength of TF3 (reference treatment) after single dose administration in healthy subjects under fasting conditions 	
Secondary Objectives:	

 • To further investigate the PK of tepotinib 	

- To further assess the safety and tolerability of tepotinib TF3 under fasting conditions

Exploratory Objectives:

- To investigate the PK of tepotinib metabolites
- To explore the effect of pharmacogenetics (PGx) and variations of associated genes on the PK profile of tepotinib (if applicable).

Methodology: This is an open-label, single-dose, randomized, 2-period, 2-sequence cross-over, single-center trial to investigate the bioequivalence of the 100 mg and 250 mg dose strengths of tepotinib tablet formulation 3 under fasted condition.

For each subject, the study consists of a screening period (Day -21 to Day -2) and 2 treatment periods including a washout of 21-days in each period. Eligible subjects will be admitted to the clinical unit on Day -1. Subjects who continue to meet the eligibility criteria will be randomized to 1 of 2 treatment sequences on Day 1 of Period 1.

In each study period, the subjects will be hospitalized from Day -1 to Day 4 for safety assessments and PK blood sampling and return to the site on Days 5 - 8 for additional PK blood sampling and monitoring of AEs and concomitant medication. Study drug will be administered on Day 1 of each period. An End of Trial Visit will be performed at the end of Period 2 (21 days after dosing in Period 2).

Planned number of subjects:

18 subjects.

Primary Endpoints:

- Area under the plasma concentration-time curve (AUC) from time zero (= dosing time) to the last sampling time at which the concentration is at or above the lower limit of quantification (AUC_{0-t}), AUC from time zero extrapolated to infinity ($AUC_{0-\infty}$) and maximum plasma concentration (C_{max}) of tepotinib observed from time zero to 168 h post-dose of each period.

Secondary Endpoints:

- Time to reach C_{max} (t_{max}), terminal half-life ($t_{1/2}$), apparent total body clearance considering the fraction of dose absorbed (CL/f) and apparent volume of distribution during terminal phase (V_z/f) of tepotinib observed from time zero to 168 h post-dose of each period
- Occurrence of treatment-emergent adverse events (TEAEs; incidence, frequency, intensity and causality), occurrence of changes in safety laboratory assessments, 12-lead electrocardiograms (ECGs) and vital signs.

Exploratory Endpoints:

- PK profiles of tepotinib metabolites: AUC_{0-t} , $AUC_{0-\infty}$, C_{max} , t_{max} , $t_{1/2}$ of tepotinib metabolites observed from time zero to 168 h post-dose of each period
- Genetic variants and mutations in genes that potentially influence PK of tepotinib.

Pharmacokinetics:

Plasma concentrations of tepotinib and its metabolites MSC2571109A and MSC2571107A will be determined in each study period from pre-dose until 168 h post-dose. PK parameters will be calculated using non-compartmental analysis.

Pharmacogenetics: PGx analysis on Day -1 of Period 1**Other assessments:** Not applicable**Diagnosis and key inclusion and exclusion criteria:**

Healthy males and females (of non-childbearing potential) between 18 to 55 years (inclusive) with a body mass index (BMI) ≥ 18.5 and $\leq 29.9 \text{ kg/m}^2$ and a total body weight between 50 and 100 kg (inclusive) at the time of Screening examination may be enrolled in the trial.

Investigational Medicinal Product: dose/mode of administration/ dosing schedule:

- Tepotinib film-coated tablet TF3 containing 100 mg of drug substance for oral administration (test treatment)
- Tepotinib film-coated tablet TF3 containing 250 mg of drug substance for oral administration (reference treatment)

Administration of single doses of 500 mg tepotinib per treatment period, administered as 2 tablets of 250 mg, and 5 tablets of 100 mg, after overnight fasting.

The washout period between single doses will be at least 21 days.

Reference therapy: dose/mode of administration/dosing schedule: Not applicable**Planned trial and treatment duration per subject:**

About 9 weeks each from Screening to End of Trial Visit, including 2 treatment periods of 21 days each.

Statistical methods:**Primary Endpoints:**

An analysis of variance (ANOVA) model will be fitted to the log-transformed PK parameters C_{max} , AUC_{0-t} , $AUC_{0-\infty}$ based on the PK analysis set. The model will include treatment, period, sequence as fixed effects and subject within sequence as random effect.

Treatment differences on the log scale of tepotinib will be estimated for C_{max} , AUC_{0-t} , $AUC_{0-\infty}$ together with their 90% CIs.

The null hypothesis of non-bioequivalence will be rejected if the 90% CI for the ratio of the geometric mean lies within the bioequivalence acceptance interval of 0.8000 to 1.2500 for all primary PK parameters.

Secondary and exploratory endpoints will be analyzed with summary statistics.

Table 1 **Schedule of Assessments**

Assessment/ Activity	Screening	All periods				End of Trial Visit
Day	-21 to -2	-1	1	2 - 4	5 - 8	21 (± 1) after dosing in Period 2
Written informed consent ^a						
Hospitalization		X -----		X		
Ambulatory visits	X				X	X
In-/exclusion criteria	X	X (Period 1 only)				
Randomization			X (predose, Period 1 only)			
Demographic data (incl. height, weight, BMI)	X					
Medical history	X					
Physical examination	X	X		Day 2, Day 4 ^e		X
Vital signs (blood pressure, pulse rate, body temperature)	X	X	pre-dose, 2 h, 8 h	Day 2, Day 4 ^e		X
12-lead safety ECG	X	X	pre-dose ^b , 2 h, 8 h	Day 2, Day 4 ^e		X
Clinical laboratory (hematology, biochemistry, urinalysis)	X	X	pre-dose	Day 2, Day 4 ^e		X
Coagulation	X					
Serology (HIV/hepatitis)	X					
Pregnancy test (in serum at Screening and End of Trial Visit, in urine on Day -1)	X	X				X
Urine drug screen; Alcohol breath test	X	X				
Administration of tepotinib			X			
PK blood sampling			X ^c	X ^c	X ^c	
PGx blood sampling		X (Period 1 only)				
Adverse events monitoring	X	X ←-----→ X ^d				
(Prior and) concomitant medication	X	X ←-----→ X ^d				

BMI = body mass index, ECG = electrocardiogram, h = hours, HIV = human immunodeficiency virus, min = minutes, PK = pharmacokinetics, PGx = pharmacogenetics

- a Written informed consent must be obtained prior to any screening activities
- b ECGs at pre-dose will be recorded in triplicate
- c PK blood samples for determination of tepotinib and its metabolites will be collected at pre-dose (within 60 min prior to dosing) and 15, 30, 45, 60, 90 min, and 2, 3, 4, 6, 8, 12, 16 and (Day 2) 24, 36, (Day 3) 48, 60, (Day 4) 72, (Day 5) 96, (Day 6) 120, (Day 7) 144 and (Day 8) 168 h post-dose
- d Adverse events and concomitant medication will be assessed from signing of the informed consent form throughout the whole study until End of Trial.
- e All safety assessments on Day 4 before discharge.

2 Sponsor, Investigators and Trial Administrative Structure

This clinical trial will be sponsored by:

Merck Healthcare KGaA an affiliate of Merck KGaA, [name].

Single trial site at ^{PI} [REDACTED], Germany.

The Principal Investigator ^{PI} [REDACTED], ^{PI} [REDACTED], Germany) will provide expert medical input and advice relating to trial design and execution and is responsible for the review and signoff of the clinical trial report consistent with the International Council for Harmonisation (ICH) Topic E6 Good Clinical Practice (GCP; hereafter referred to as ICH GCP) [7].

Signature pages for the Protocol Lead and the Principal Investigator as well as a list of Sponsor responsible persons are in [Appendix I](#).

The trial will appear in the following clinical trial registries: European Union Clinical Trials Register (EudraCT), ClinicalTrials.gov.

Nuvisan GmbH, [name], a contract research organization (CRO), will conduct the clinical part of the trial including trial set-up, coordination, safety and analytical lab, monitoring, data capture, data management, statistical analysis, and clinical trial reporting. Nuvisan GmbH will also submit the necessary applications to the applicable Independent Ethics Committee (IEC) and regulatory bodies on behalf of and in close alignment with the Sponsor.

Laboratory sample processing, handling, and storage instructions will be presented in a separate Lab Manual which will be prepared by Nuvisan GmbH in cooperation with the Sponsor. Monitoring and data management procedures will be defined in separate Monitoring and Data Management Plans which will be prepared by Nuvisan GmbH.

The Sponsor will provide the Investigational Medicinal Product (IMPs) tepotinib. Packaging, labeling and distribution of all IMPs to the trial site will be conducted by a designated contract manufacturing organization (Nuvisan GmbH). The Sponsor will supervise all outsourced activities.

3 Background Information

The mesenchymal-epithelial transition factor (c-Met), along with its ligand, the hepatocyte growth factor (HGF) have been implicated in carcinogenesis and metastatic tumor progression, because of their ability to enhance angiogenesis, cancer cell proliferation, migration and invasion, as well

as conferring resistance to apoptosis. Pharmacological interference with the HGF/c-Met axis is considered as a promising strategy to inhibit primary tumor growth and metastasis.

In primary pharmacodynamic studies, tepotinib (MSC2156119J) potently inhibited c-Met kinase activity in a dose-dependent manner. This inhibitory effect was confirmed both in tumor cells expressing full-length c-Met upon stimulation with HGF, and in tumor cells in which c-Met was activated in a ligand independent manner, ie in cells harboring c-Met gene amplification or expressing the oncogenic fusion protein translocated promoter region (TPR) Met.

Until 19-July-2019, 715 subjects have been exposed to tepotinib at doses up to 1400 mg, including 195 healthy participants, and 12 subjects with Child-Pugh class A or B hepatic impairment in 8 Clinical Pharmacology studies.

Four of the Clinical Pharmacology studies in healthy subjects (EMR200095-007, n = 27; EMR200095-0012, n = 24; MS200095-0039, n = 12 and MS200095-0044, n = 66) were conducted as single-dose studies with 500 mg tepotinib, in one study (EMR200095-002, n = 28), single doses of 30 mg tepotinib were administered to healthy subjects. In two further studies, healthy subjects received multiple doses of 500 mg tepotinib over 11 days (MS200095-0030, n = 12) or 8 days (MS200095-0032, n = 20).

In all 7 studies performed in healthy subjects, the subjects well tolerated single doses of 30 mg or 500 mg tepotinib, or multiple doses of 500 mg tepotinib. All treatment-emergent adverse events (TEAEs) were mild to moderate, except 2 Grade 3 asymptomatic lipase elevations in 2 subjects, and 2 Grade 3 TEAE (back pain and collum femoris fracture) that were not considered related to treatment. TEAEs did not show a pattern across the trials. No drug-related serious adverse events (SAEs) were reported and no subject died. No clinically significant findings regarding laboratory parameters, vital signs and electrocardiogram (ECG) including corrected QT interval according to Fridericia (QTcF) were noted.

In a further Clinical Pharmacology trial (MS200095-0028), 6 subjects with Child-Pugh Class A, 6 subjects with Class B hepatic impairment, and 6 healthy subjects received single doses of 500 mg tepotinib. No subject had serious adverse events, Grade ≥ 3 TEAEs, or discontinued due to a TEAE, or died during the study

In 2 clinical studies (EMR200095-001 and EMR200095-003), 161 patients with different solid tumors received multiple doses up to 1400 mg tepotinib. In 2 studies, 138 patients with hepatocellular cancer (EMR200095-004 and EMR200095-005) received multiple doses of 300 mg, 500 mg or 1000 mg tepotinib. In a clinical study in patients with MET-positive, non-small-cell lung cancer (NSCLC) harboring epidermal growth factor receptor mutations (EMR200095-006), 64 patients received multiple doses of 300 mg or 500 mg tepotinib.

Until 19-July-2019, 145 patients with NSCLC in the ongoing VISION trial (MS200095-0022) have received multiple doses of 500 mg tepotinib.

Elevations in serum lipase and amylase are identified risks for tepotinib and were observed in healthy subjects and patients exposed to tepotinib. These increases were mild to moderate in severity (exception: 1 Grade 3 lipase elevation), transient and without apparent dose dependency. All increases of serum amylase/lipase were asymptomatic and not associated with pancreatitis.

This study will investigate the bioequivalence of tepotinib tablet formulation 3 (TF3) administered as 5 tablets of 100 mg versus 2 tablets of 250 mg dose strength. A dose of 500 mg once daily is the recommended Phase 2 dose. Refer to the Investigator's Brochure (IB) for further information about the nonclinical and clinical programs and the implemented Guidance for the Investigator.

For the PK of tepotinib refer to the IB.

3.1 Trial Rationale

This trial will investigate the bioequivalence of the 100 mg dose strength (test treatment) of the envisioned market formulation, TF3, compared to the 250 mg dose strength of the same formulation (reference treatment), both given at a single dose of 500 mg. The 250 mg dose strength of TF3 had been shown to be bioequivalent to the 500 mg dose strength of TF2, used in the Phase 2 studies, and in a previous bioequivalence study (MS200095-0044).

While the recommended clinical dose of 500 mg for the treatment of patients with NSCLC can be administered using the 250 mg dose strength, the lower TF3 dose strength of 100 mg will be made available for individual dose adaptation and future development options.

The tablet cores of both TF3 dose strengths are identical. The tablet film-coating is a non-functional coating that differs only marginally in composition between both dose strengths. However, owing to the different tablet sizes, the difference of coating material per surface area formally exceeds regulatory thresholds in certain regulatory regions. Clinical investigation of bioequivalence between the TF3 strengths will therefore be performed.

The trial design using an open-label 2-period, 2-sequence cross-over design under fasted conditions follows the regulatory guidelines of the Food and Drug Administration (FDA) [1, 2], the European Medicines Agency (EMA) [3] and the Pharmaceuticals and Medical Devices Agency (PMDA) [4, 5].

This clinical trial will be conducted in compliance with the clinical trial protocol, ICH GCP [7], and any additional applicable regulatory requirements.

Based on the available nonclinical and clinical data to date, the conduct of the trial specified in this protocol is considered justifiable.

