6.1 Description of the Investigational Medicinal Products

Investigational Medicinal Products:

Tepotinib (MSC2156119J), 3-(1-{3-[5-(1-Methyl-piperidin-4-ylmethoxy)-pyrimidin-2-yl]-benzyl}-1,6-dihydro-6-oxo-pyridazin-3-yl)-benzonitrile hydrochloride hydrate (HCl), is supplied as

- 250 mg white-pink, oval, biconvex tablet with embossment “M” on one side TF3 for oral administration (reference treatment)

Tepotinib 250 mg film-coated tablets (TF3) have a drug load of approximately 30% and contain the excipients D-mannitol, microcrystalline cellulose, crospovidone, magnesium stearate, silica colloidal anhydrous, and Opadry® II pink.

- 100 mg white-yellow, round, biconvex tablets with embossment “M” on one side TF3 for oral administration (test treatment).

Tepotinib 100 mg film-coated tablets (TF3) have a drug load of approximately 30% and contain the excipients D-mannitol, silica colloidal anhydrous, crospovidone, magnesium stearate, and Opadry II yellow.

All excipients used in the tablet formulations are of compendial grade. Supplier’s certificates show that there is no transmissible spongiform encephalopathy risk. Tepotinib is provided in aluminum (ALU/ALU) blisters and storage is at or below 25°C.

For dosage and administration see Section 6.2.

Reference product: Not applicable.

Specific rules for treatment modifications: Not applicable.

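### Does the mismatch between the identical-core statement and the two excipient lists undermine the comparison of the 100 mg and 250 mg tablets?

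*Protocol*

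**What the plan says.** Section 3.1 (Trial Rationale) explains why a clinical study is needed. It says that "The tablet cores of both TF3 dose strengths are identical" and, of the coat, that "The tablet film-coating is a non-functional coating that differs only marginally in composition between both dose strengths". It adds that, because the tablets differ in size, the amount of coating relative to tablet surface passes a formal limit in some regions, and that bioequivalence is therefore tested in subjects.

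Section 6.1 describes the two products. The 250 mg tablets "contain the excipients D-mannitol, microcrystalline cellulose, crospovidone, magnesium stearate, silica colloidal anhydrous", followed by the pink Opadry II coat. The 100 mg tablets "contain the excipients D-mannitol, silica colloidal anhydrous, crospovidone, magnesium stearate, and Opadry II yellow". Both are given a drug load of about 30%.

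The primary objective (Section 4.1) and the hypotheses (Section 8.1) compare five 100 mg tablets with two 250 mg tablets under fasting. Neither mentions cores or coats.

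**The concern.** In a bioequivalence trial the identity of the test product matters. The coat is named separately in each list, so microcrystalline cellulose reads as a core ingredient. "Identical" cannot refer to size or content, because the strengths differ; it can only refer to composition, and composition is where the lists disagree. Both sentences are complete and grammatical, so this does not look like redaction or a fault of text extraction.

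Two readings follow. If the lists are right, test and reference differ in their cores, and the account in Section 3.1 of a coating question only is incomplete. If Section 3.1 is right, Section 6.1 misdescribes the test tablet.

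Three consequences could then be feared:

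- The trial answers a different question from the one posed.
- Subjects are screened for hypersensitivity against an incomplete excipient list.
- The planning assumptions (ratio 0.95, CV from Part A of the earlier study) rest on a false premise.

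**Working it through.** **1. The lists side by side (Section 6.1), coat set aside**

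| Excipient | 250 mg (reference) | 100 mg (test) |
|---|---|---|
| D-mannitol | yes | yes |
| Microcrystalline cellulose | yes | no |
| Crospovidone | yes | yes |
| Magnesium stearate | yes | yes |
| Silica colloidal anhydrous | yes | yes |

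The 250 mg list has one ingredient that the 100 mg list lacks. The 100 mg list has none that the 250 mg list lacks. No amounts are given, so the share of tablet mass involved cannot be worked out.

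**2. Does the trial's question change?** The parameter in Section 8.1 is the ratio of geometric means, test over reference, for the tablets as administered. The rule in Section 8.6.2 is that the 90% CI must lie within 0.8000 to 1.2500 for all three PK parameters. Neither depends on why the products might differ. If a core difference moved the true ratio outside the limits, that would be a case of the null hypothesis, and the test limits the chance of wrongly declaring equivalence to 5% per parameter whatever the cause. A ratio further from 1 than 0.95 but still inside the limits would cost the sponsor power, not validity.

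**3. Does eligibility change?** Exclusion criterion 10 (Section 5.3.2) covers hypersensitivity to excipients in general. Under Section 6.2 each subject is due to receive both products. The excipients to consider are therefore those of the two lists together, and microcrystalline cellulose is already among them through the 250 mg tablet. Adding it to the 100 mg list would exclude nobody further.

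**4. Do the planning assumptions depend on identical cores?** Section 8.2 takes CV = 15.77% from Part A of MS200095-0044, which compared TF3 with TF2, two different formulations. It takes a ratio of 0.95, which already allows a 5% difference. Neither figure is derived from the core statement in Section 3.1.

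The stated power was also reproduced. Inputs from Section 8.2: n = 16 evaluable, ratio 0.95, one-sided alpha 0.05. Limits: ln 0.80 = -0.2231 and ln 1.25 = 0.2231. For a 2x2 crossover,

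- s_w = sqrt(ln(1 + CV²))
- SE = s_w × sqrt(2/n)
- df = n - 2 = 14

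Power is the exact probability that both one-sided t-tests reject, found by integrating over the chi-square distribution of the estimated variance.

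| CV | s_w | SE | Computed power | Protocol |
|---|---|---|---|---|
| 15.77% | sqrt(ln(1.02487)) = 0.1567 | 0.1567 × sqrt(2/16) = 0.0554 | 90.2% | about 90% |
| 18.4% | sqrt(ln(1.03386)) = 0.1825 | 0.1825 × sqrt(2/16) = 0.0645 | 80.4% | about 80% |

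Both figures hold, and no input to them comes from the product description.

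**5. Which reading is likelier?** Section 3.1 states outright that the cores are the same and treats the strengths as one formulation. In Section 6.1 the drug load is the same, the other four non-coat ingredients match, and the 100 mg list names nothing in place of the missing one. This points to an omission from a sentence, although the protocol alone cannot prove it.

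**The case for a change.** The best case for acting is that the identical-core statement forms part of the argument for running the trial, and that the protocol goes to the ethics committee and to health authorities (Sections 9.6 and 9.7). One of two sections is wrong about a product under comparison, and setting it right would need only one lookup and a one-line edit. It can fairly be added that no charitable reading removes the mismatch: if microcrystalline cellulose were part of the coat instead, the claim that the coats differ only marginally would come under strain.

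The factual part of this stands: the sections disagree, and one of them needs tidying. The consequences do not stand. Section 3.1 explains why a clinical comparison was judged necessary. If the cores did differ, the comparison would still be needed, and only the explanation would need rewording. The actual composition is a matter for the product's own documentation; Section 9.7 names the IMP dossier among the papers for the authorities. An error in the protocol's descriptive list does not alter which tablets are supplied and swallowed.

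**Conclusion.** The inconsistency is real but clerical: one excipient appears in the 250 mg list and not in the 100 mg list, against a statement that the cores are the same. Whichever side is wrong, the correction is a line of descriptive text. It changes no treatment given, eligibility decision, endpoint, hypothesis, sample size, model or decision rule, and the stated power of about 90% (about 80% at CV 18.4%) stands. No change to the plan is called for.

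This rests on two assumptions. The first is that the tablets supplied are the intended TF3 products, so that the fault lies in the wording and not in the supply; nothing in the protocol suggests otherwise. The second is that microcrystalline cellulose belongs to the core. That is an inference from the coat being named separately, since Section 6.1 does not label core and coat. If it fails, the mismatch moves to the coat, and the conclusion about the analysis is the same.
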